Participants with reactive or indeterminate result resulting from either assisted or unassisted methods will be encouraged to get a confirmatory test at a health facility. A confirmatory test will also be suggested for participants with non-reactive result. The difference between these two result groups will be the level of encouragement given to do the confirmatory test. While participant with reactive or indeterminate results will be strongly encouraged, participants with a non-reactive result will be suggested for a confirmatory test. These suggestions are derived from Indonesia's current guideline on HIV detection, where the confirmatory test is to be done at the health facility using the HIV blood test.

Figure 1. Study Flowchart

[figure not shown]

Table 3. Global Fund HIV testing targets in 23 districts for 2019-2020

No	Province	Districts	Region	Target of HIV Testing			
				P3	P4	P5	P6
1	Sumatera Utara	Kota Medan	1	904	904	1,002	1,002
2	Sumatera Utara	Kab. Deli Serdang	1	406	406	450	450
3	Sumatera Selatan	Kota Palembang	1	1,371	1,371	1,520	1,520
4	Lampung	Kota Bandar Lampung	1	393	393	435	435
5	Banten	Kota Tangerang Selatan	1	223	223	247	247
6	Banten	Kab. Tangerang	1	820	820	909	909
7	DKI Jakarta	Kota Jakarta Selatan	1	536	536	594	594
8	DKI Jakarta	Kota Jakarta Timur	1	877	877	973	973
9	DKI Jakarta	Kota Jakarta Pusat	1	1,341	1,341	1,486	1,486
10	DKI Jakarta	Kota Jakarta Barat	1	1,318	1,318	1,461	1,461
11	DKI Jakarta	Kota Jakarta Utara	1	1,431	1,431	1,586	1,586
12	Jawa Barat	Kota Bogor	2	474	474	525	525
13	Jawa Barat	Kota Bekasi	2	248	248	275	275
14	Jawa Barat	Kota Bandung	2	582	582	645	645
15	Jawa Barat	Kota Depok	2	374	374	415	415
16	Jawa Tengah	Kota Semarang	2	510	510	565	565
17	Jawa Tengah	Kota Surakarta	2	172	172	190	190
18	Jawa Timur	Kota Malang	3	84	84	93	93
19	Jawa Timur	Kota Surabaya	3	1,173	1,173	1,300	1,300
20	Bali	Kota Denpasar	3	1,407	1,407	1,559	1,559
21	Sulawesi Selatan	Kota Makassar	3	1,444	1,444	1,600	1,601
22	Papua Barat	Kota Sorong	4	438	438	485	485
23	Papua	Kota Jayapura	4	786	786	871	871

Table 4. Achieved target of HIV testing per semester in 23 priority districts (2018-2019)

No	Kab/Kota	Region	Achieved target of HIV testing per semester
1	Kota Denpasar	3	982
2	Kota Makassar	3	866
3	Kota Palembang	1	694
4	Kota Jakarta Utara	1	612
5	Kota Medan	1	575
6	Kota Surabaya	3	568
7	Kota Jakarta Barat	1	544
8	Kota Bandung	2	487
9	Kota Jakarta Timur	1	479
10	Kota Jakarta Pusat	1	473
11	Kota Jakarta Selatan	1	448
12	Kota Sorong	4	415

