Sample size requirements for the third question measurement pertains to the number of FSW who test positive for HIV at a health facility and are thus eligible to initiate treatment. This will depend upon (1) the number of FSW presenting at health facilities for testing and (2) the positivity rate among those tested. Sample sizes should thus be calculated accordingly. If we assume a testing positivity rate of 3%, it is apparent that the expected number of FSWs who would be eligible for treatment will be small and we will lack sufficient statistical power to make meaningful comparisons with comparison districts. For this reason, it is recommended that the impact of community screening among FSW be measured using SIHA data for FSW in both intervention and comparison districts. This estimate of impact derived in this way will be confounded if it were to be the case that interventions other than HIV self-testing were to be better implemented in intervention vs. comparison districts. It might be possible to minimize this potential bias by including measures of intervention implementation performance in the intervention and comparison districts in multivariable analyses. Thus, a large enough sample size is required to ensure sufficient power to determine the difference in the intervention and control districts.

C. THE INTERVENTION

1. General Description of The Intervention

FSW who meet the eligibility criteria will be offered for HIV blood test first. Participants who wish to take the test will then managed according to the current guideline for standard of care. Participants who disagree to take HIV blood test will then be offered screening test with Ora-Quick®. There will be with two options for community HIV screening by Peer Leaders: (1) in a convenient community setting assisted by PL/PE (assisted screening) or (2) in a setting of their own choosing without assistance from PL/PE (unassisted screening). FSW will also be able to access a community-based screening test by following online link from messages spread through WhatsApp number without having to come into contact with outreach workers. The saliva-based Ora-Quick® test kit will be used for community screening.

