- f. For clients with reactive community screening results, (i) advise them (online) to get a confirmatory test at selected health facility (ii) offer to facilitate making an appointment for testing to accompany them to a health facility for testing, and (iii) provide FSW with a referral card to be submitted to the health facility. Another possible option is to have the referral cards within the test kit, therefore when FSW with reactive results do not wish for their result to be revealed other than towards the post-test survey platform and health officers, they can access health facility for confirmatory test. Information on what's needed to be done when one finds reactive test result has to be mentioned in detail within the instructional fliers or video.
- g. For clients with non-reactive community screening results, (i) again online reinforce prevention measures, (ii) remind them of the need for periodic testing and (iii) offer a referral card in case FSW want a confirmatory test at a health facility (if there is concern about the accuracy of the community screening test). In the case where referral card is included within every box containing test kit, FSW with non-reactive result might still be able to bring the card to selected health facility to get a confirmatory test.

4. Implementation Guidelines for Control Group (Standard Program)

For the control group, there will be no new interventions implemented (that is, they will continue with “business as usual”). In each control site, there is an implementing unit (IU) responsible for conducting outreach for FSWs. The outreach target is set up for one year, meaning that a sex worker will only be outreached once in a year. The outreach packet should include condoms and lubricant distribution as well as HIV-AIDS education media distribution. Furthermore, each IU also has a certain number of HIV tests to fulfill every six months. To achieve the target, the IU should reassure sex workers to do HIV test at least once every six months. While it is possible for a sex worker to have HIV test in three months interval, only one test is count for a sex worker every six months. The test could be conducted at health facilities or mobile clinics. A mobile clinic could be conducted at any place where convenient to the participants, such as workplace or living space. For FSWs with reactive test results, they will then be referred to health facility to start on ART.

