In the event that participants' data are collected by paper, a procedure to upload the data into the established online system will be developed. Each data manager in the IUs needs to conduct the procedure regularly. This is to ensure that all data are being captured thoroughly.

F. DATA ANALYSES

The data analyses to be undertaken will be directed to addressing the research questions laid out at the beginning of the protocol and statistical tests appropriate to each specific analysis will be performed to inform the interpretation of results. The specific steps in the data analysis will be as follows:

1. Compare the characteristics of FSWs who receive self-testing and blood testing.

2. Compare the characteristics of FSWs who receive assisted and unassisted self-testing.
3. Compare proportion of FSWs taking confirmatory test out of those who receive the test in the assisted and unassisted self-testing.
4. Compare the proportion of FSWs who receive HIV test out of those who got offered for the test (including self-testing) in the intervention group with proportion of FSWs who receive HIV test in the control group.
5. Compare the proportion of FSWs taking confirmatory test (including self-testing) out of those receive the test in intervention groups and control group.
6. Compare the proportion of HIV positive in the assisted, unassisted (intervention) and HIV positive in the control group.
7. Compare the proportion of ART initiation in the assisted, unassisted (intervention) and the control group.
8. Calculate the cascade of HIV testing and treatment.
9. Compare stigma scores and FSWs who went to a health facility for HIV testing between assisted, unassisted group.
10. Compare the HIV and STI risk behaviors between assisted and unassisted group.

G. CONTINGENCY STUDY DESIGN

Should the OraQuick® test kits not become available in sufficient time to conduct a full-scale cRCT, a smaller-scale study will instead be undertaken. The purpose of the smaller study is the same as the cRCT described above, and the same protocol described above will be implemented. But the comparison is achieved targets between before and after intervention – there will be no comparison districts. The study will be undertaken in three (3) districts. The three districts will be selected from different parts of Indonesia, and they are: Kota Bandung (west part of Indonesia), Kota Denpasar (central part of Indonesia), and Kota Makassar (center-east part of Indonesia).

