The primary limitations of the smaller-scale study are (1) the districts were not randomly chosen and (2) the proportion of HIV testing before and after intervention that might not sufficient to produce a statistically significant result to prove the success of the intervention. This smaller-scale version of the study should be viewed as a demonstration or pilot project leading to a bigger study afterwards.

Data analysis will be done by comparing changes in outcome variables measured against results in the four semesters prior to the study in the 3 districts compared to the other 20 acceleration districts.

Analysis of outcome variables are similar with the cRCT approach as below:

1. Compare the characteristics of FSWs who receive self-testing and blood testing in 3 districts.
2. Compare the characteristics of FSWs who receive assisted and unassisted self-testing 3 districts.
3. Compare proportion of FSWs taking confirmatory test in the assisted and unassisted self-testing 3 districts.

4. Compare the proportion of FSWs who receive HIV test including self-testing in the intervention group with proportion of FSW who receive HIV test in the control group (in 3 districts before the intervention and other 20 acceleration districts).
5. Compare the proportion of FSWs taking confirmatory test (including self-testing) in the intervention group with proportion of FSW who receive HIV test in the control group (in 3 districts before the intervention and the other 20 acceleration districts).
6. Compare the proportion of HIV positive in 3 districts (assisted and unassisted) and HIV positive in the control group (in 3 districts before the intervention and other 20 acceleration districts).
7. Compare the proportion of ART initiation in 3 districts (assisted and unassisted) and the control group (in 3 districts before the intervention and other 20 acceleration districts).
8. Calculate the cascade of HIV testing and treatment.
9. Compare stigma scores and FSW who went to a health facility for HIV testing.
10. Compare the HIV and STI risk behaviors.

H. RESEARCH ETHICS AND PERMISSION

[figure not shown]

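### Contingency step 5 sets confirmatory testing on one side against any HIV test on the other, with no base for either, so its result could mislead in either direction

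*Combined protocol and SAP*

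**What the plan says.** Section G (Contingency Study Design) applies if the kits are late. It keeps the purpose of the main trial and introduces its analysis steps with "Analysis of outcome variables are similar with the cRCT approach as below".

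- **Section G, step 5** compares women "taking confirmatory test (including self-testing) in the intervention group with proportion of FSW who receive HIV test in the control group". The control data are described as "in 3 districts before the intervention and the other 20 acceleration districts". No denominator is given for either group, and the parenthesis about self-testing is not explained.
- **Section G, step 4** has the same control-side endpoint, but its intervention side matches it: "Compare the proportion of FSWs who receive HIV test including self-testing in the intervention group".
- **Section F, item 5**, the parallel step of the main design, reads: "Compare the proportion of FSWs taking confirmatory test (including self-testing) out of those receive the test in intervention groups and control group". It names one endpoint and one base for both groups.
- **Section C.1** says who can reach a self-screen: "Participants who disagree to take HIV blood test will then be offered screening test with Ora-Quick".
- **Section B.1** extends confirmatory testing beyond reactive screens: "A confirmatory test will also be suggested for participants with non-reactive result".
- **Section C.4** says of testing in the standard programme: "The test could be conducted at health facilities or mobile clinics".
- **Section E.3** records, in a separate row and for both groups, the women who agreed to a facility test and actually had it.

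**The concern.** In this protocol a confirmatory test is the facility blood test that follows a community screen. Only women who first declined the blood test are offered that screen. On its plain wording, the intervention side of step 5 therefore leaves out every woman who accepted a facility test at first offer, whereas the control side counts every woman who received any test. The two proportions describe different events in different groups of women, and their difference does not estimate an effect.

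Objective 2 (section A.6) asks whether community screening raises HIV testing at health facilities. Step 4 cannot answer this because it counts self-tests. Steps 3, 8 and 9 touch on confirmatory or facility testing but name no control group. Step 5 is left as the one intervention-versus-control step that could answer it. If its wording allows several readings with opposite signs, the choice among them could be made after the data are seen.

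**Working it through.** The documents give no expected result for step 5 and no sample size for the contingency design, so there is no planned figure to reproduce. The check asks what each reading of step 5 would show when facility testing has truly risen.

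Inputs:

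- C, the proportion tested in the control data: 0.5, the planning value in section B.5.
- First-offer facility testing in the intervention group: set equal to C, so that any true gain comes only from confirmatory tests.
- s, the share of decliners who self-screen: 0.6, **assumed**.
- c, the share of screened women who take a confirmatory test: 0.3, **assumed**.

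The documents give no value for s or c. The ranges tried were C 0.3 to 0.7, s 0.3 to 0.9 and c 0.03 to 0.9.

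Per woman offered testing:

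- Screened: (1 - C) × s = 0.5 × 0.6 = 0.30
- Confirmed: 0.30 × 0.3 = 0.09
- All provider-given blood tests: 0.50 + 0.09 = 0.59
- True difference: 0.59 - 0.50 = **+9 points**

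| Reading of the intervention side | Value | Against 0.50 | Over the assumed ranges |
|---|---|---|---|
| A. Confirmatory tests per woman offered | 0.09 | -41 points | -70 to +27 |
| B. Confirmatory tests per woman screened | 0.30 | -20 points | -67 to +60 |
| C. First-offer tests plus self-tests, per woman offered | 0.50 + 0.30 = 0.80 | +30 points | +9 to +63 |
| D. First-offer plus confirmatory blood tests, per woman offered | 0.59 | +9 points | +0.3 to +57 |

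When the sign changes:

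- Reading A shows a loss when (1 - C) × s × c is below C. At C = 0.5 or above this always holds, since s × c is below 1. At C = 0.3 with s = c = 0.9, 0.7 × 0.81 = 0.567, and the result is a gain of about 27 points.
- Reading B shows a loss only when c is below C. At c = 0.6 it gives 0.60 - 0.50 = +10 points, against a true difference of 0.5 × 0.6 × 0.6 = +18 points.
- Reading C depends on first-offer tests being counted as well. If self-screened women count but first-offer testers do not, the result is 0.30 - 0.50 = -20 points.

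Only reading D returns the true difference, and the text of step 5 does not state it.

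**The case against.** The best defence is that an analyst would know what was meant. Section G says its purpose is that of the main trial, objective 2 names facility testing, and section G separately states the governing comparison as the change from the four prior semesters in the 3 districts against the other 20. If the parenthesis means facility blood tests including those that follow a self-test, nothing is mismatched. That is reading D. It is possible, but step 5 does not say it, and the other readings fit the words at least as well.

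Three further points stand in part.

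- Section F item 5 is an imperfect benchmark. Control women receive no self-screen, so a confirmatory test after screening has no counterpart there. Copying item 5 into section G would not repair step 5.
- The rates s and c are assumptions, so the table illustrates and does not predict.
- The step belongs to a fallback that the plan itself regards as a pilot.

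A reader might infer that step 5 would necessarily show a large loss. The documents do not support that: the sign depends on the unstated base, on uptake and confirmation rates that are not given, and on the unexplained parenthesis. High confirmation cannot be excluded, since section C.5 pays for confirmatory visits after both reactive and non-reactive screens.

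A reader might also take baseline rates from Tables 4 and 5: 2 × 2,335 / 9,947 = 46.9% in the three districts and 2 × 7,440 / 43,025 = 34.6% in the other 20. The sums are right, but these are tests per woman reached, may include mobile-clinic tests, and can count a woman twice in a year. They are not proportions of women tested at a facility.

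**Conclusion.** Step 5 of section G is not like-for-like as worded. It names different endpoints on the two sides and no base on either, and so does not estimate the effect on facility testing that objective 2 asks about. At the plan's control rate of 0.5, with the assumed 60% screening and 30% confirming, a true +9 points could be reported as -41, -20 or +30. The direction of the error is therefore not fixed. That the sides do not match follows from the text alone; the sizes rest on the assumed rates and on first-offer testing staying at the control level.

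The point should be corrected before the contingency design is used. It does not touch the randomised design, and it does not mean that section G ignores facility testing after screening elsewhere: steps 3, 8 and 9 bear on it, though without a control comparison.

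**What to change.** Replace step 5 with a comparison that uses the same definition on both sides.

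- **Endpoint:** provider-given HIV blood tests, meaning first-offer tests plus confirmatory tests after self-screening. Count mobile-clinic tests the same way in both groups and in the prior semesters. Self-tests alone do not count here; step 4 covers them.
- **Base:** FSW reached, or FSW offered testing, chosen now and used throughout, with a stated rule for women who enter through the online link without outreach contact (section C.1). The documents show past outreach counts by year and past test counts by semester, so the time unit must also be fixed.
- **Contrast:** the change from the four prior semesters in the 3 districts, against the same change in the other 20.
- **Confirmatory uptake after self-screening:** keep it as an intervention-only description, as in step 3. Record it for reactive and non-reactive results. The main table in section E.3 lists it for reactive screens only; the additional list for the unassisted approach covers both.

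The cost is the rewording of one step and slightly more recording for assisted screening. The main limit is that historical counts may not separate facility from mobile-clinic tests. The documents do not show that facility-only counts exist for the earlier semesters, and section E.3 itself notes limitations in facility data. If they cannot be separated, the result should be reported as provider-given testing and not as facility testing.

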Annex 1. Flowchart of Routine Data Recording

Annex 2. Eligibility Form

Eligibility Participants Form for Intervention

To be completed by PL/PE during FSW outreach

These checklists are to be completed by PL/PE during FSW outreach to assess the eligibility of FSW to participate in this study. If questions number 1-7 is answered “Yes”, then participant is eligible for the study. If question number 8 is answered “Yes”, then participant is not eligible for the study, but eligible for “blood test study in health facility”.

No	Criteria inclusion	Yes	No
1	Female, aged 18 years old or more		
2	Admit having transactional sex (vaginal, oral, or anal) at least once within the last one month		
3	Have never had any HIV test taken within the last 6 months		
4	Self-reported HIV Negative OR HIV status unknown		
5	Agreed to participate in this study		
6	Not currently participating in any other HIV prevention study		
7	After being offered for HIV testing in health facility, participant stated: A. Agree for HIV testing in health facility* B. Not agree for HIV testing in health facility**		

Note:

* Use information form for VCT

** Use information form for OFT

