P_1 = the expected population proportion in the comparison group of districts (set = 0.5 – this is the worst-case scenario and will produced a sample size that is adequate irrespective of the actual proportion)

P_2 = the expected population proportion in the intervention group of districts (set = 0.6 – assume minimum effect size to be realized of 10 percentages points)

$$P = (P_1 - P_2) / 2$$

$(P_1 - P_2)$ = the magnitude of comparison-group differences (or change over time) to be detected with the specified level of precision and power (assumed to be +/- 10 percentage points)

deft = design effect to compensate for clustering at the district level (1.5 assumed).

The required sample size is thus $n \geq 635$ per experimental group; ≥ 761 after 20% allowance for lost-to-follow up

³ Source: Lwanga SK and Lemeshow S. Sample Size Determination in Health Studies: A Practical Manual. Geneva: World Health Organization.

Interpretation: we would need to recruit 761 FSW who self-test for HIV testing in the intervention districts and 761 FSW for HIV testing at health facilities in comparison districts to be able to detect a 10 percentage point difference in the rate of HIV testing at health facilities (intervention vs. comparison districts) to have 95% certainty that a difference of that magnitude would not have occurred by chance and 90% certainty of detecting a difference of this magnitude if such a difference existed.

In order to assess whether “assisted” or “unassisted” community HIV screening among FSW results in a larger increase in the rate of HIV testing at health facilities, we would need samples of size $n \geq 761$ each of FSW who received assisted and unassisted screening in intervention districts, a total of $n \geq 1,522$ FSW in intervention districts, plus $n \geq 761$ in comparison districts.

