- How likely is it that the client will get a HIV test at a health facility as a result of the community screening test, on a scale of 1-5
- Comments and suggestions.

3. Routine Recording

Because of limitations in the data recorded and reported by health facilities, the study will rely primarily upon data recorded by IU outreach staff. Modifications will be made to the data recording and reporting systems currently being used to facilitate collection of the data needed for the study in a manner that minimizes additional recording and reporting burden. The nature of the adjustments to be made will be different for "assisted" and "unassisted" community screening.

To capture the data needed for of this study, the following data need to be recorded:

No	Data Recorded	Intervention Group	Control Group
1	Number of FSW contacted via outreach that were at least 6 months since their last HIV test for whom testing at a health facility was recommended	Yes	Yes
2	Numbers of FSW offered for HIV test at health facility	Yes	Yes
3	Numbers agreeing and disagreeing to testing at a health facility	Yes	Yes
4	Of those agreeing to getting tested at a health facility, the numbers that actually went to a health facility and were tested for HIV	Yes	Yes
5	Number of FSW offered for OFT screening	Yes	No
6	Among FSW not agreeing to be tested at a health facility, the numbers that agreed to (1) assisted community HIV screening and (2) unassisted community HIV screening	Yes	No
7	Numbers that were actually screened, assisted and unassisted	Yes	No
8	The number of community screening tests that were reactive	Yes	No
9	Among FSW with reactive community screening tests, the numbers that were subsequently tested at a health facility	Yes	No
10	Number of FSW initiating ART	Yes	Yes

For **unassisted** approach, additional information will be gathered as indicated below:

1. Numbers of FSW who access the link online
2. Numbers of FSW who are deemed eligible
3. Numbers of FSW who fill in baseline survey and agree to participate
4. Numbers of FSW who agree to take HIV test at health facility
5. Numbers of FSW who request the kit being delivered vs picking-up at fixed location
6. Numbers of FSW who upload the test result
7. Numbers of reactive vs non-reactive test result
8. Numbers of FSW who complete the post-test survey

9. Among FSW with community screening tests, the numbers that were subsequently tested at a health facility (reactive OR non-reactive)
10. Number of FSW initiating ART

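### Annex 2 cannot be applied as printed, and the plan supports two incompatible intervention populations: all eligible women offered facility testing, or only those who self-test

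*Combined protocol and SAP*

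**What the plan says.** Annex 2 carries the title "Eligibility Participants Form for Intervention" and is completed by peer workers during outreach. Its instruction makes a woman eligible when items 1 to 7 are all Yes. For a Yes on a question 8 it gives this consequence: "then participant is not eligible for the study, but eligible for" a blood-test study at a health facility. The printed list ends at item 7, which sits under the inclusion criteria and reads "After being offered for HIV testing in health facility, participant stated: A. Agree for HIV testing in health facility* B. Not agree for HIV testing". The footnote to answer A is "Use information form for VCT"; answer B goes to the oral-fluid form.

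The inclusion and exclusion criteria in Section B.3 do not mention the response to the facility-test offer.

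Section B.5 plans on facility-testing proportions of 0.5 in comparison districts and 0.6 in intervention districts. It then interprets the sample size as follows: "we would need to recruit 761 FSW who self-test for HIV testing in the intervention districts and 761 FSW for HIV testing at health facilities". The second 761 are the comparison-district women. For assisted versus unassisted screening it asks for 761 of each, 1,522 in total, in intervention districts.

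Section E.3, row 3, records "Numbers agreeing and disagreeing to testing at a health facility" in both groups.

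**The concern.** Two things are wrong on the face of the form. A Yes-to-all rule cannot be applied to an item answered A or B, and the exclusion rule points to a question that is not there. Outreach staff in 15 intervention districts would have to settle this for themselves, and might do so differently.

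The larger issue is which women form the intervention arm. The blood-test wording suggests that the women sent out of the study are those who agree to facility testing. B.5 leans the same way, because in the outreach route the oral-fluid test is offered only after the facility test is declined. A woman's answer to that offer comes after her district was allocated and is closely tied to the planning outcome, facility testing. If it selects women in one arm and not in the other, the randomised comparison of districts is lost for that outcome. The 0.5 and 0.6 inputs would also describe a different population from the one recruited.

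**Working it through.** **1. The plan's own figure.** Inputs from B.5: proportions 0.5 and 0.6, power 90% (Z = 1.282), design effect 1.5, loss 20%. The pooled proportion is taken as the mean, 0.55.

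n = [Z × √(2 × 0.55 × 0.45) + 1.282 × √(0.5 × 0.5 + 0.6 × 0.4)]² / 0.1²

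- With one-sided Z = 1.645: n = 422.03, rounded up to 423. Then 423 × 1.5 = 634.5 (stated 635), and 634.5 × 1.2 = 761.4 (stated 761).
- With the printed Z = 1.96: n = 518.04, and 518.04 × 1.5 = 777, which does not match. That is a separate matter and nothing below depends on it.

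What matters here is the unit. The two proportions are defined as population proportions in the two groups of districts, but the 761 in the intervention arm is then counted in women who self-test.

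**2. The passages side by side.**

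| Points to self-testers as the intervention population | Points to all eligible women offered facility testing |
|---|---|
| Annex 2 instruction on the missing question 8 | Annex 2 footnotes: A to the VCT form, B to the oral-fluid form |
| B.1: consent to the community screening study follows refusal of the blood test | B.3: refusal is not a criterion |
| B.5: 761 (or 1,522) women who self-test | C.5: incentive for women who take VCT and report the result |
| E.4(c): taking part once means receiving the kit, testing and reporting | E.3 rows 1 to 4: contacted, offered, agreeing, and actually tested, in both groups |
| F, analyses 6 and 7: intervention arm written as assisted and unassisted | F, analysis 1 (self-test versus blood test) and analysis 4 (those offered the test, in the intervention arm) |
| | Annex 4: baseline survey headed for blood-test and self-test participants; Annex 5: follow-up of women choosing the blood test |

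The two columns cannot both define the arm.

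**3. Why the choice matters (illustration only).** Assumptions:
- a share *a* of women agrees to facility testing in both arms;
- refusers in comparison districts are not facility-tested;
- agreers complete testing at rate c = 0.50/a, so the comparison rate is 0.50;
- a share q of intervention refusers is facility-tested after the oral-fluid offer;
- every intervention refuser self-screens.

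The intervention rate among all offered is a × c + (1 - a) × q = 0.50 + (1 - a) × q. For a true effect of +10 points, q = 0.10/(1 - a). Comparing only the intervention refusers with all comparison women gives q - 0.50.

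| a | q | True effect (points) | Apparent effect (points) |
|---|---|---|---|
| 0.5 | 0.20 | +10 | -30 |
| 0.6 | 0.25 | +10 | -25 |
| 0.7 | 0.33 | +10 | -17 |
| 0.8 | 0.50 | +10 | 0 |
| 0.9 | 1.00 | +10 | +50 |

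The result is sensitive to the last assumption. If only 60% of refusers self-screen and all of their facility tests come from that 60%, the self-screeners' rate is q/0.60. At a = 0.5 this is 0.20/0.60 = 0.33, an apparent -17 points. At a = 0.7 it is 0.333/0.60 = 0.56, an apparent +6 points.

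**The case against.** The best defence is that the study named in Annex 2 means only the community screening study of Section B.1. On that reading the instruction merely separates an oral-fluid stream from a blood-test stream, and the footnotes give both streams forms. The surveys, incentive, routine counts and analyses in the right-hand column above all keep the women who agree. This stands, and it rules out several stronger readings that a reader might infer:

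- **That agreers will be dropped from the intervention arm.** The documents do not say so. That question 8 refers to agreers is itself inferred from the blood-test wording, and it may be a leftover cross-reference.
- **That self-testers are all refusers.** C.1 and C.3 also let women reach screening through an online link without meeting an outreach worker, and Annex 2 is written for outreach contacts.
- **That comparison districts keep every eligible woman.** E.3 rows 1 to 4 suggest it, but no comparison-district eligibility rule is stated.
- **That the trial's result will change sign.** No step in Section F specifies self-testers against all comparison women on facility testing. B.5 also calls 0.5 a worst case, not an expected rate.

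Figure 1, the Annex 1 flowchart and the consent form are not visible in the copy reviewed and could show which reading was intended.

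The defence does not make the Annex 2 rule usable, does not align the B.5 recruitment unit with the rates it is sized for, and does not explain the intervention arm as written in analyses 6 and 7.

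**Conclusion.** The point holds as an unresolved contradiction about the analysis population. The form's rule is wrong as written, the B.5 intervention target is counted in a different unit from the proportions behind it, and different sections place different women in the intervention arm.

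The possible bias is conditional. It arises only if self-testers are set against all comparison-district women on facility testing. Under the assumptions in the working, a true +10 points would then appear as -30 at 50% agreement, 0 at 80% and +50 at 90%. The documents give neither the agreement share nor the uptake after self-screening, so these figures show sensitivity and do not predict the trial's error. The matter should be settled before enrolment, because women left out under a misread form would have no individual baseline data to recover later.

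**What to change.** - **Annex 2:** define eligibility as Yes on items 1 to 6. Delete or correct the sentence on question 8. Move item 7 below the eligibility line as the recorded outcome of the offer, with A going to the VCT forms, B to the oral-fluid forms, and both counted.
- **B.5:** for intervention versus comparison, state the target in both arms as eligible women offered facility testing. Keep the numbers of assisted and unassisted self-screeners as a separate target.
- **Section F:** use the same all-offered denominator for the between-arm comparisons in analyses 5 to 7, as analysis 4 does for its intervention arm, and state it for the control arm of analysis 4 too. Proportions among women tested can still be reported descriptively.

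The cost is a one-page form correction and a few sentences of text. E.3 rows 2 to 4 already collect the counts in both groups. There are two burdens. The consent sequence in B.1 and Section H, described there only for the screening routes, must be reconciled so that it clearly covers women who take the facility test. Progress must also be tracked on women offered testing as well as on kits used.
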